6.1.1 Considerations regarding countries

Variation between different countries and sites are expected due to variation in geography and climate and thus grass exposure which may affect assessments. Further, variation in standard treatment procedures, and possible differences in the conduct of the trial are expected to vary between countries. Variation between sites (centres) is also expected but is assumed to be small compared to the variation between countries. The major source of variability is expected to be pollen exposure. Some sites can have very few subjects making it unreasonable to include sites as a covariate in the analysis model. In this trial, country is used as a covariate in the models.

6.1.2 IMP discontinuation

As pointed to previously, reasons for discontinuation of IMP will be categorised into three categories: 1) due to "IMP-related AE" 2) due to "lack of efficacy" and 3) due to "other reasons". As the eCRF defined that trial- and treatment discontinuation reasons are not corresponding to this tripartite split the following mapping form the observed data in the eCRFs to the three categories will be performed:

Treatment discontinuation reasons presented in the eCRF's "Visit Status"-form are:

• Severe or persistent symptoms of eosinophilic oesophagitis

- Pregnancy
- Physician's decision
- Adverse event(s)
- Asthma difficult to control
- Treatment is unblinded

while withdrawal from trial reasons presented in eCRF's "End of study"-form are:

- Screening failure
- Withdrawal of consent
- Adverse event(s)
- Lost to follow-up
- Non-compliance with protocol
- Pregnancy
- Death
- Lack of efficacy
- Randomisation code broken
- Other

Before DBL, the discontinuation of treatment is re-defined and the subject specific list of discontinuations and their classifications to fit the estimand framework is in supplementary document to the SAP: Documentation of Trial Analysis Sets.

Discontinuation due to AEs

A subject is considered discontinued from the treatment due to IMP-related AE if the following conditions are met:

- 1. If, in the "Visit status"-form or End of study"-form reported reason for treatment discontinuation or withdrawal from trial is:
 - Severe or persistent symptoms of eosinophilic oesophagitis
 - Adverse event(s)
 - Asthma difficult to control
- 2. And AEs related to discontinuation are classified as possibly or probably related.

Discontinuation due to lack of efficacy

A subject is considered discontinued from the treatment due to lack of efficacy if the following conditions are fulfilled:

1. If, in the "End of study"-form, it is noted that the subject withdrawal from trial due to "Lack of efficacy".

Discontinuation due to "other reasons"

A subject is considered discontinued from the treatment due to other reasons if the subject discontinues treatment or withdrawal from trial due to other reasons than mentioned above.

Date: 27-Oct-2023 Version: 1.0 Status: Final Page: 21 of 47

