5 SUBJECT DISCONTINUATION

5.1 Discontinuation from IMP treatment

Subjects must be discontinued from IMP treatment under the following circumstances:

- If a subject becomes pregnant
- The subject experiences severe or persistent symptoms of oesophagitis or has a confirmed diagnosis of eosinophilic oesophagitis
- The subject's asthma becomes difficult to control
- If, in the investigator's opinion, continuation with IMP treatment would be detrimental to the subject's well-being
- If treatment is unblinded for the subject or investigator

For all subjects discontinued from IMP, efforts must be made to have subjects attend and complete all scheduled visit procedures to collect the data for the primary and key secondary endpoints. Subjects must be educated about the scientific importance of their data, even if they discontinue trial product.

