Under the primary estimand, the assumption is that subjects who discontinue IMP due to "lack of efficacy" would not have experienced a treatment benefit other than that observed in the placebo arm. Contrary, subjects discontinuing for either of the two other reasons would have experienced a treatment benefit similar to the observed among subjects randomised to the same treatment arm.

These considerations imply that under the primary estimand, the only observed data used for analysis are obtained before discontinuation of IMP, while data obtained after discontinuation will be treated as missing. It further follows that imputation of missing data or data treated as missing will condition on the reason for discontinuation as outlined above. Moreover, data can be missing even for subjects not discontinuing IMP (e.g. due to low compliance). The reasoning for this type of missingness is ignorable and, consequently, this missing data will be imputed under the assumption that subjects experience a treatment benefit similar to that observed among subjects randomised to the same treatment arm. For further details, see section 6.2.1.

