3.2 Study design

This is a phase III, randomised, parallel-group, double-blind, placebo-controlled trial of 5-grass mix SLIT-drops in adults with grass pollen-induced moderate to severe allergic rhinoconjunctivitis, with or without asthma. The trial was conducted over two grass pollen seasons.

A total of 440 adult subjects were planned to be randomised (1:1) to continuously receive either active treatment (grass SLIT-drops) or placebo treatment once daily

All subjects should receive daily treatment continuously from at least 16 weeks before the anticipated start of the 1st EGPS through the 2nd EGPS (definitions are provided in Section 9.1), corresponding to approximately 26 months of treatment (see Figure 1). Open-label rescue medication for AR/C was provided during the GPS. The subjects were asked to complete a RQLQ diary at V3 during the off-season for grass and tree pollen and then weekly during the EGPSs. The subjects were furthermore asked to fill in an eDiary daily during the EGPSs to capture information on rhinitis and/or conjunctivitis symptoms, use of symptom-relieving medications, and impact of rhinitis and/or conjunctivitis quality of life.

Figure 1 Trial design

Data for the primary endpoint were collected by the subjects by completing questions related to their daily symptoms and medication use in an electronic diary (eDiary).

No interim analysis was planned.

Routine safety surveillance was conducted throughout the trial. The follow-up visit was conducted via a telephone call approximately one week after the end of trial visit.

The first subject was randomised 15-Aug-2022 and subjects were planned to received treatment for 26 months. A total of 445 subjects were randomised and dosed.

Statistical analysis plan Trial ID: SU-G-01	Date: Version:	27-Oct-2023 1.0
EudraCT No.: 2020-000455-12	Status:	Final
CONFIDENTIAL	Page:	15 of 47

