6.2.1 Handling of intercurrent events and missing data for the trial product estimand – main approach

The relevant endpoints will be compared between treatment groups using the trial product estimand with population FAS and data point DPS1. This means that subjects for whom the endpoint is missing (the exclusion of daily diary data due to discontinuation of trial treatment) will still be included in the analysis through multiple imputations under the hypothetical situation where subjects continued to take trial treatment as planned. The missing data imputation is done using the following rules:

• For subjects that discontinue trial treatment due to lack of efficacy, multiple imputation of the missing endpoint will be taken from the placebo group. This assumes that had the subject continued to take trial treatment, they would have experienced similar efficacy to subjects in the placebo arm. Data are assumed to be missing not at random (MNAR).

Statistical analysis plan Trial ID: SU-G-01 EudraCT No.: 2020-000455-12 CONFIDENTIAL	Date: Version: Status: Page:	27-Oct-2023 1.0 Final 22 of 47		
---	---------------------------------------	---	--	--

- For subjects that discontinue trial treatment due to IMP-related AEs, multiple imputation of the missing endpoint will be taken from their own treatment group. This assumes that the level of efficacy that would have been experienced by the subject if they had continued to take trial treatment is unrelated to the occurrence of the AE and, if they had continued to take trial treatment, they would have experienced similar efficacy to subjects in their own treatment group irrespective to randomised treatment. Data is assumed to be missing at random (MAR).
- For subjects that discontinue trial treatment due to any other non-IMP-related reason or subjects that have missing data but completed the trial, multiple imputation of the missing endpoint will be from their own treatment group. This assumes that the level of efficacy that would have been experienced by the subject had they continued to take trial treatment is not related to their discontinuation of trial treatment. Data is assumed to be MAR.

In summary, missing data is imputed based on the following observed on-treatment data (Table 5):

Table 5: Sources of observed data used for imputation under the primary estimand.

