6.5 Changes and/or deviations to protocol-planned analyses

Several changes were made to the statistical analysis described in the trial protocol. The list of changes is summarised in this section:

- PP analysis set is removed from analysis sets used in this trial. This analysis set does not align with the estimand framework; therefore, it will not be used in this trial.
- Safety and tolerability objectives and endpoints are added as supportive secondary endpoints.
- As described in the estimand framework, the most important IE is the discontinuation of IMP. The IMP discontinuation was not collected in the relevant manner in eCRF. Discontinuation of IMP is then re-classified based on reported IMP discontinuation and trial withdrawal reason (see Section 6.1.2), and these re-classified reasons are used in the estimand framework.
- In this trial, subjects were stratified based on their history of asthma in adulthood. During the trial, it was determined that it is most relevant for interpretation of the disease and treatment is ongoing asthma status at screening. Therefore, the asthma status at screening will be used in the analysis models instead of asthma strata. Twenty one subjects were stratified as asthmatics but did not have ongoing asthma at screening. Subjects with ongoing asthma are expected to be well-balanced between treatment arms.
- In the protocol, the primary and key secondary endpoint estimator contains the trial site/country as a random effect. In SAP, county and year interaction is a random effect. The change accounts for the variability of pollen load yearly in each country.
- In the protocol, the proposed MCID is 0,16. Since the protocol proposal, additional research was performed and based on published results presented new MCID for PGPS is 0,1 and EGPS 0,22 (**Blaiss et al. 2022**).
- Pollen season end date and pollen peak definition a modified to add clarity. Pollen season end date is specified that it is the last day of the last occurrence of 3 consecutive days with pollen count larger or equal to 10 grains/m³. For the peak season it is specified the 14 consecutive days period is used as a peak.

7 Sample size determination

General considerations

In this trial, primary and secondary endpoints will be tested hierarchically to control the familywise error rate at 5% level. Individual endpoint analyses will be based on treatment comparisons using a 2-sided t-distributed test on a 5% level of significance.

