The power calculations were done in two steps. This sample size wasthen evaluated using the estimand framework. The power was calculated for both the primary endpoint (TCS) and the key secondary endpoint (RQLQ). It is expected that the treatment difference in overall RQLQ during peak season is greater than the MCID of 0.10 and during entire season greater than 0.22 (Blaiss et al. 2022).

TCS power calculation

The estimated TCS mean, standard deviation and treatment differences during the peak season from three trials is presented in Table 8. The power calculation is based on a TCS treatment difference of 21% (1.64 in absolute value) and a common standard deviation of 5.5. Under these assumptions, the trial has a power of 80% with the sample size of 180 evaluable subjects. The power is 86% for the primary estimand and 80% for the secondary estimand with the assumption that 10% out of 220 subjects will discontinue the trial, with 4.5% of subjects discontinuing due to AEs and 1% due to lack of efficacy each year.

Trial	Placebo $\mu(\sigma)$	Active $\mu(\sigma)$	Difference absolute (relative)
GT-08 2006	8.44 (5.48)	5.14 (4.06)	3.3 (39%)
P05238	7.74 (6.50)	6.10 (5.09)	1.64 (21%)
P08067	5.73 (5.03)	4.56 (4.60)	1.17 (20%)
Average			2.04

Table 8: Mean and standard deviation of TCS during the peak of a season.

RQLQ power evaluation

The estimated RQLQ mean, standard deviation and treatment differences during the peak season from 3 trials raw data is presented in Table 9 below.

Table 9: Mean and standard deviation of RQLQ during the peak of a season.

Trial	Placebo $\mu(\sigma)$	Active $\mu(\sigma)$	Difference Absolute (relative)
GT-08 2005	1.82 (1.11)	1.37 (0.97)	0.45 (25%)
GT-08 2006	1.48 (1.05)	1.05 (0.91)	0.43 (29%)
P05238	1.73 (1.34)	1.41 (1.12)	0.33 (18%)
P08067	1.73 (1.34)	1.18 (1.08)	0.15 (11%)
Average	0.34		

A common standard deviation of 1.15 has been assumed in the power evaluation. An expected placebo mean is 1.60 and an expected treatment difference is 0.34. With 180 evaluable

Statistical analysis plan
Trial ID: SU-G-01
EudraCT No.: 2020-000455-12
CONFIDENTIAL

subjects per treatment arm, the power of 98% is reached for testing if RQLQ treatment difference is greater than proposed MCID of 0.1. The power is 95% for the primary and 92% secondary estimands for the sample size of 220 subjects with the same discontinuation assumptions as for TCS.

Conclusion

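### Active-arm subjects who stop IMP for lack of efficacy but stay in the trial are classed as 'other' and imputed from the active arm, contrary to the primary estimand

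*SAP*

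**What the plan says.** **The estimand.** Protocol 15.1.1 names stopping trial treatment, for an adverse event or for lack of efficacy, as the intercurrent event. SAP 3.1.1.1 also defines it as discontinuation of trial treatment. Under the primary (trial product) estimand, SAP 3.1.1.2 assumes that subjects who stop IMP for lack of efficacy "would not have experienced a treatment benefit other than that observed in the placebo arm". Diary data after the stop are treated as missing.

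**The classification.** SAP 6.1.2 sorts IMP stops into three groups using two eCRF forms.
- The Visit Status form offers six reasons for stopping treatment. Lack of efficacy is not one of them.
- The End of study form, which records withdrawal from the trial, does list it.
- The lack-of-efficacy group has one condition: on the End of study form, "it is noted that the subject withdrawal from trial due to" lack of efficacy.
- The adverse-event group draws on both forms.
- Every remaining stop is 'other reasons'.

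**The imputation.** SAP 6.2.1 and Table 5 impute lack-of-efficacy stops from placebo. "For subjects that discontinue trial treatment due to any other non-IMP-related reason", the subject's own arm is used. Table 6, the sensitivity analysis for the same estimand, moves only IMP-related adverse-event stops to placebo. Active 'other' stops still draw from active.

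**Retention.** Protocol 5.1 states: "For all subjects discontinued from IMP, efforts must be made to have subjects attend and complete all scheduled visit procedures".

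**Disclosure.** SAP 6.5 acknowledges: "The IMP discontinuation was not collected in the relevant manner in eCRF". It refers back to the mapping in 6.1.2 and adds no rule for subjects who stop IMP but remain in the trial.

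**The concern.** The estimand turns on why a subject stopped IMP. The rule that implements it turns on whether the subject also left the trial. Take two active subjects who stop on the same day because the treatment is not working. The one who withdraws is imputed from placebo. The one who does what protocol 5.1 asks and stays is imputed from active, and so is credited with a benefit that SAP 3.1.1.2 says that subject would not have had.

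What is at stake is the main estimator of the primary estimand, on which the whole testing hierarchy rests. No planned trial product analysis varies the own-arm assumption for 'other' stops by itself, although protocol 15.14 promised sensitivity analyses addressing the assumptions behind the main estimators. The disposition summary in SAP 8.3 will also report reasons under the same three groups, so the label carries into reporting.

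**Working it through.** **Inputs.**
- Test (SAP section 7): "2-sided t-distributed test on a 5% level of significance".
- Effect and SD (SAP section 7): "The power calculation is based on a TCS treatment difference of 21% (1.64 in absolute value) and a common standard deviation of 5.5".
- Size: 440 planned, 1:1 (SAP 3.2), so 220 per arm; 180 evaluable per arm.
- Planned discontinuation (SAP section 7): each year 4.5% for adverse events and 1% for lack of efficacy.

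**Step 1: reproduce the stated power.** The documents give no formula for power by estimand. I assume the effect is diluted by the share of active subjects imputed from placebo over two years. Power = Φ(δ/SE − 1.96), with SE = 5.5 × √(2/n).

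| Case | n per arm | δ | Power | Stated |
|---|---|---|---|---|
| Observed cases | 180 | 1.64 | 80.8% | 80% |
| Primary estimand, 2 × 1% to placebo | 220 | 1.64 × 0.98 = 1.607 | 86.5% | 86% |
| Secondary estimand, 2 × 5.5% to placebo | 220 | 1.64 × 0.89 = 1.460 | 79.5% | 80% |
| No lack-of-efficacy stop recognised | 220 | 1.64 | 87.8% | not stated |

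The stated 86% is consistent with lack-of-efficacy stops being imputed from placebo, as the estimand intends.

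**Step 2: who can be affected.** All of these must hold.
1. The subject is in the active arm. Placebo subjects are imputed from placebo under every label (Table 5).
2. The subject stopped IMP for lack of efficacy but is not recorded as withdrawn from the trial for that reason.
3. The subject has no on-treatment diary entry in the peak season concerned. One entry is enough for an observed average (SAP 6.2, and subject 2 in SAP 6.2.5).
4. The stop came before the end of that season. SAP 6.2 handles gaps in earlier seasons without regard to the stop.

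**Step 3: size per subject.** The expected imputed value is the active mean instead of the placebo mean, a difference of 1.64 under the planning assumption. The active-arm mean, and so the treatment difference, moves by 1.64/220 = 0.0075 TCS points. SE = 5.5 × √(2/220) = 0.52.

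| Affected active subjects (assumed) | Shift favouring active | In SE units |
|---|---|---|
| 1 | 0.0075 | 0.01 |
| 4 (about 2%) | 4 × 0.0075 = 0.03 | 0.06 |
| 11 (5%) | 11 × 1.64/220 = 0.08 | 0.16 |
| 22 (10%) | 22 × 1.64/220 = 0.16 | 0.31 |

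This is on the untransformed scale of the sample size section.

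**Step 4: no true effect.** The active and placebo pools then have the same expected mean. Replacing 1.64 by 0 gives an expected shift of 0, whatever the number mislabelled.

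**The case against.** **Planned analyses already cover it.** The tipping-point analysis (SAP 6.2.7.1) adds a penalty to all imputed active values in steps of 0.5 TCS. Penalties of 1.5 and 2.0 bracket the planned 1.64, so they remove the benefit from adverse-event and 'other' imputations together. That is harsher than moving 'other' alone. The treatment policy estimand uses the actual diaries of subjects who stop IMP and stay, and its sensitivity analysis (SAP 6.2.4) imputes missing endpoints from placebo for every treatment stop. This stands as partial cover. But the tipping point neither corrects the main estimate nor isolates this assumption. The treatment policy analyses answer a different question, and a retained subject with diary entries is observed there, so the imputation in dispute does not arise.

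**The pre-lock list may already correct it.** SAP 6.1.2 refers to a subject-level classification in a supplementary document, which is not among the documents reviewed. Individual cases may have been handled there. But the SAP states no criterion for departing from the form-based rule, so a reader cannot rely on it.

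**Judgement.** SAP 6.1.2 shows coded reasons only, and reading lack of efficacy into a physician's-decision code trades a reproducible rule for opinion. This is fair, and it limits reclassification to cases where the recorded data show the reason.

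**Size.** A reader might take the planned 1% per year as the rate of mislabelling. The documents do not support that: SAP section 7 gives it as a share of subjects who discontinue the trial, and the End of study rule already catches those. A reader might also suppose that a sizeable part of the 'other' stops are really lack of efficacy. No figure in the documents supports any such share.

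**Conclusion.** The mismatch is real: it is a stated rule that does not deliver the stated estimand, and it affects a path the protocol encourages. If active is truly better, the main estimate is overstated by about 0.0075 TCS points per affected subject. This assumes that the planned difference of 1.64 holds between the two imputation pools, with 220 subjects per arm. The number affected is unknown, so the totals for 4, 11 and 22 subjects are illustrations, not estimates. Even 11 subjects would move the result by only 0.16 of a standard error.

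A reader might infer that the rule always favours active, or that it inflates the type I error. Neither follows: with no true effect the expected shift is nil, so the rule can enlarge an existing effect but does not create one on average. Nor do the documents show that the primary conclusion would change. The case for acting is that the primary analysis should do what its estimand says, and that the repair is cheap.

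**What to change.** 1. **SAP 6.1.2.** Define the lack-of-efficacy group by the reason for stopping IMP, whether or not the subject left the trial. Apply this in the blinded pre-lock list wherever the recorded data show that reason, for example behind a 'Physician's decision' or 'Other' code. State the criterion in the SAP.
2. **SAP 6.2.2.** Add a trial product sensitivity analysis that imputes active 'other' IMP discontinuations from placebo, otherwise as in the main approach.

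The cost is a short blinded review that may involve some judgement, and one extra run of existing code. The added sensitivity estimate will be slightly conservative, because some 'other' stops have nothing to do with efficacy. If the data are already unblinded, the second item can still be reported as post hoc and marked as such, as protocol section 15 requires.

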6.2 Analyses

The main estimator and sensitivity estimator for both estimands will be based on an identical method of statistical analysis .The estimator for all estimand will be based on MMRM with treatment, year, treatment and year interaction, and ongoing asthma status as fixed effects and country and year interaction as random class effect (more details specified Section 9.5.2). Exposure to pollen can vary yearly; thus, treatment effects may differ each year. Therefore, the model contains treatment and year interaction as a fixed effect. Pollen count depends on local geography and weather and can vary locally yearly. Thus, the model comprises country and year interaction as a random effect.

The actual data used in each analysis may vary according to the different strategies taken for the handling of IEs and missing data. In the trial product estimand, data until treatment discontinuation will be included in the analysis and treatment policy estimand all observed data will be included.

Imputations will be done on the average scores, but not daily/weekly values. To calculate an average score, only one observation is needed.

Missing data will be imputed by sampling from an appropriate pool that matches the subject's characteristics. Missing data for 1st year will be imputed from observed data in 1st year, and missing data for 2nd year will be imputed from the observed data in 2nd year. Thus, PGPS data will be imputed from observed PGPS data and EGPS from observed EGPS. Missing data for subjects with ongoing asthma will be imputed from subjects with ongoing asthma for subjects without ongoing asthma will be imputed from subjects without ongoing asthma following the rules defined below.

If the IE occurred after 1st season, then the missing data imputation in the 1st year will be handled disregarding the IE and imputed under assumption MAR (data will be imputed from the subject's own treatment arm for both estimands). The missing data of 2nd season will be handled based on IE. If IE occurred after 2nd, the missing data will be handled disregarding IE in both seasons. For more details, see Sections 6.2.1 and 6.2.2.

The imputation pool of subjects will consist of subjects with all and partially observed data. In other words, if subject will be used in the analysis, they will also be used in the pool of the subjects to impute from.

Rubin's (Rubin 1987) multiple imputation strategy will be used to pool results of multiple analysis.

6.2.1 Handling of intercurrent events and missing data for the trial product estimand – main approach

The relevant endpoints will be compared between treatment groups using the trial product estimand with population FAS and data point DPS1. This means that subjects for whom the endpoint is missing (the exclusion of daily diary data due to discontinuation of trial treatment) will still be included in the analysis through multiple imputations under the hypothetical situation where subjects continued to take trial treatment as planned. The missing data imputation is done using the following rules:

• For subjects that discontinue trial treatment due to lack of efficacy, multiple imputation of the missing endpoint will be taken from the placebo group. This assumes that had the subject continued to take trial treatment, they would have experienced similar efficacy to subjects in the placebo arm. Data are assumed to be missing not at random (MNAR).

Statistical analysis plan Trial ID: SU-G-01 EudraCT No.: 2020-000455-12 CONFIDENTIAL	Date: Version: Status: Page:	27-Oct-2023 1.0 Final 22 of 47		
---	---------------------------------------	---	--	--

- For subjects that discontinue trial treatment due to IMP-related AEs, multiple imputation of the missing endpoint will be taken from their own treatment group. This assumes that the level of efficacy that would have been experienced by the subject if they had continued to take trial treatment is unrelated to the occurrence of the AE and, if they had continued to take trial treatment, they would have experienced similar efficacy to subjects in their own treatment group irrespective to randomised treatment. Data is assumed to be missing at random (MAR).
- For subjects that discontinue trial treatment due to any other non-IMP-related reason or subjects that have missing data but completed the trial, multiple imputation of the missing endpoint will be from their own treatment group. This assumes that the level of efficacy that would have been experienced by the subject had they continued to take trial treatment is not related to their discontinuation of trial treatment. Data is assumed to be MAR.

In summary, missing data is imputed based on the following observed on-treatment data (Table 5):

Table 5: Sources of observed data used for imputation under the primary estimand.

Missing data	Missing data or data treated as missing in 2022, 2023 or in both years.		Observed data as source for bootstrap: sampling from subjects with complete 1 st and 2 nd year data for the pollen- period under consideration	
Randomised treatment	Discontinuation reason	Ongoing asthma status at screening	Randomised treatment	Ongoing asthma status at screening
Active	Lack of efficacy ^A	Yes	Placebo	Yes
Active	IMP-related AEs ^A	Yes	Active	Yes
Active	Other ^A	Yes	Active	Yes
Active	Data is missing ^B	Yes	Active	Yes
Active	Lack of efficacy ^A	No	Placebo	No
Active	IMP-related AEs ^A	No	Active	No
Active	Other ^A	No	Active	No
Active	Data is missing ^B	No	Active	No
Placebo	Lack of efficacy ^A	Yes	Placebo	Yes
Placebo	IMP-related AEs ^A	Yes	Placebo	Yes
Placebo	Other ^A	Yes	Placebo	Yes
Placebo	Data is missing ^B	Yes	Placebo	Yes
Placebo	Lack of efficacy ^A	No	Placebo	No
Placebo	IMP-related AEs ^A	No	Placebo	No
Placebo	Other ^A	No	Placebo	No
Placebo	Data is missing ^B	No	Placebo	No

^A: Data is either (actually) missing or treated as missing because of "earlier" treatment discontinuation

^B: Data is missing prior to any observed date of treatment discontinuation

6.2.2 Handling of intercurrent events and missing data for the trial product estimand – sensitivity analysis

The sensitivity analysis for the trial product estimand will use the multiple imputation policy described above for the main analysis except:

 For subjects that discontinue the trial treatment due to IMP-related AEs, multiple imputation of the missing endpoint will be from the placebo group. This assumes subjects reporting IMP-related AEs would have experienced a level of efficacy similar to subjects in the placebo group if they had continued to take trial treatment. Data is assumed to be MNAR. See Table 6.

Table 6: Sources of observed data used for imputation under the sensitivity analyses of the primary estimand.

Missing data	a or data treated as miss or in both years.	sing in 2022, 2023	Observed data as source for bootstrap: sampling from subjects with complete 1 st and/or 2 nd year data for the pollen-period under consideration	
Randomised treatment	Discontinuation reason	Ongoing asthma status at screening	Randomised treatment	Ongoing asthma status at screening
Active	Lack of efficacy ^{\$}	Yes	Placebo	Yes
Active	IMP-related AEs ^A	Yes	Placebo	Yes
Active	Other ^A	Yes	Active	Yes
Active	Data is missing ^B	Yes	Active	Yes
Active	Lack of efficacy ^A	No	Placebo	No
Active	IMP-related AEs ^A	No	Placebo	No
Active	Other ^A	No	Active	No
Active	Data is missing ^B	No	Active	No
Placebo	Lack of efficacy ^A	Yes	Placebo	Yes
Placebo	IMP-related AEs ^A	Yes	Placebo	Yes
Placebo	Other ^A	Yes	Placebo	Yes
Placebo	Data is missing ^B	Yes	Placebo	Yes
Placebo	Lack of efficacy ^A	No	Placebo	No
Placebo	IMP-related AEs ^A	No	Placebo	No
Placebo	Other ^A	No	Placebo	No
Placebo	Data is missing ^B	No	Placebo	No

^A: Data is either (actually) missing or treated as missing because of "earlier" treatment discontinuation

^B: Data is missing prior to any observed date of treatment discontinuation

Otherwise, the sensitivity analyses will be similar to the main analyses.

6.2.3 Handling of intercurrent events and missing data for the treatment policy estimand – main approach

The relevant endpoints will be compared between treatment groups using the treatment policy estimand using FAS and DPS2. For subjects discontinuing trial treatment, all diary data (including data collected after discontinuation of trial treatment) will be included in the derivation of the relevant endpoint. Subjects for whom the primary endpoint is missing will be included in the analysis through multiple imputation as follows:

 For subjects discontinuing trial treatment due to IMP-related AEs or lack of efficacy, multiple imputation of the missing endpoint will be from the placebo group. This assumes that missing data following treatment-related discontinuation of trial treatment is MNAR

Statistical analysis plan	Date:	27-Oct-2023	
Trial ID: SU-G-01	Version:	1.0	
EudraCT No.: 2020-000455-12	Status:	Final	
CONFIDENTIAL	Page:	25 of 47	

and that subjects no longer taking active treatment for these reasons would have shown similar efficacy to subjects receiving placebo.

• For subjects discontinuing trial treatment due to other reasons than IMP-related AEs or lack of efficacy reasons or subject have missing data, multiple imputation of the missing endpoint will be taken from their own treatment group. This assumes that the missing data are MAR.

Otherwise, the analyses of the secondary estimand are similar to the main analyses of the primary estimand. The summary of missing data imputation is provided in Table 7

Table 7: Sources of	of observed	data used f	for imputation	under the	secondarv	estimand.
		aata aooa i	or impatation		oooonaary	ootinnania

Missing data in 2022, 2023 or in both years		Observed data as source for bootstrap: sampling from subjects with complete 1 st and/or 2 nd year data for the pollen-period under consideration		
Randomised treatment	Discontinuation reason	Ongoing asthma status at screening	Randomised treatment	Ongoing Asthma status at screening
Active	Lack of efficacy	Yes	Placebo	Yes
Active	IMP-related AEs	Yes	Placebo	Yes
Active	Other	Yes	Active	Yes
Active	Data is missing ^A	Yes	Active	Yes
Active	Lack of efficacy	No	Placebo	No
Active	IMP-related AEs	No	Placebo	No
Active	Other	No	Active	No
Active	Data is missing ^A	No	Active	No
Placebo	Lack of efficacy	Yes	Placebo	Yes
Placebo	IMP-related AEs	Yes	Placebo	Yes
Placebo	Other	Yes	Placebo	Yes
Placebo	Data is missing ^A	Yes	Placebo	Yes
Placebo	Lack of efficacy	No	Placebo	No
Placebo	IMP-related AEs	No	Placebo	No
Placebo	Other	No	Placebo	No
Placebo	Data is missing ^A	No	Placebo	No

^A: Data is missing prior to any observed date of treatment discontinuation

The sensitivity analysis for the treatment policy estimand will use multiple imputation from the placebo group for all subjects that discontinue trial treatment regardless of the reason for discontinuation.

Statistical analysis plan	Date:	27-Oct-2023	
Trial ID: SU-G-01	Version:	1.0	
EudraCT No.: 2020-000455-12	Status:	Final	
CONFIDENTIAL	Page:	26 of 47	

6.2.4 Handling of intercurrent events and missing data for the treatment policy estimand – sensitivity analysis

The sensitivity analysis for the treatment policy estimand will use multiple imputation from the placebo group for all subjects that discontinue trial treatment regardless of the reason for discontinuation. For subject, that has missing data but completed the trial data is imputed from they own treatment arm.

